## 1. OBJECTIVES

### 1.1. Primary Objectives

- To evaluate the ability of  $^{89}\text{Zr}$ -df-IAB2M to detect localized, clinically significant (defined as:  $\geq 0.5 \text{ cm}^3$  with Gleason pattern  $\geq 4$ ) prostate cancer (PCa).

### 1.2. Secondary Objectives

- To determine the correlation of  $^{89}\text{Zr}$ -df-IAB2M PET/CT findings with pathological features (i.e. Gleason pattern, diameter and PSMA-positivity).
- To compare the *in vivo*  $^{89}\text{Zr}$ -df-IAB2M PET/CT and  $^{68}\text{Ga}$ -PSMA-HBED-CC PET/CT to mpMRI.
- To determine the sensitivity, specificity, positive predictive value (PPV), negative predictive value (NPV) of IAB2M to detect all pathologically identified PCa lesions that do not meet criteria for clinical significance (defined as:  $< 0.5 \text{ cm}^3$  with Gleason pattern  $< 4$ ).
- Determine the proportion of IAB2M positivity (as measured by SUV) versus lesion size, Gleason pattern, and PSA levels.
- Determine ability of  $^{89}\text{Zr}$ -df-IAB2M PET/CT to identify extra-prostatic extension.
- Determine ability of  $^{89}\text{Zr}$ -df-IAB2M PET/CT to identify lymph node or other extra-prostatic involvement.
- To determine the safety of  $^{89}\text{Zr}$ -df-IAB2M PET/CT and  $^{68}\text{Ga}$ -PSMA-HBED-CC PET/CT imaging.

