### Secondary endpoints

- To determine the ability of *in vivo* Zr-df-IAb2M PET/CT to correlate with pathological features (i.e. Gleason pattern, diameter and PSMA-positivity):
  - The Wilcoxon rank sum test will be used to compare lesions that were and were not identified on *in vivo* PET with respect to lesion size, immunohistochemical PSMA staining, and Gleason score (demonstrated by histopathology). This lesion based analysis will be performed in a similar fashion as described above.
- To compare the *in vivo* Zr-df-IAb2M PET/CT and Ga-PSMA-HBED-CC PET/CT to *in vivo* mpMRI:
  - The diagnostic accuracy of Zr-df-IAB2M PET/CT and Ga-PSMA-HBED-CC PET/CT imaging in patients with prostate cancer will be compared with that of mpMRI imaging by using sector-based analysis, as described by Turkbey B et al. The estimates of patient-specific sensitivity and specificity will be defined as the proportion of true-positive sectors and the proportion of true-negative sectors in each patient. Overall sensitivity and specificity will then be estimated by calculating the mean (and standard error) of these individual-

specific estimates across patients. Differences in sensitivity and specificity between modalities will then be evaluated by the Wilcoxon signed-rank test.

- To determine the sensitivity, specificity, PPV, NPV of IAB2M to detect all pathologically identified PCa lesions that do not meet criteria for clinical significance (defined as:  $< 0.5 \text{ cm}^3$  with Gleason pattern  $< 4$ ):
  - As above, but for lesions considered not to be clinically significant.
- To correlate IAB2M positivity (SUV) and lesion size:
  - The Spearman-rank correlation coefficient will be used to evaluate the association between SUV and size of the lesion (procedure for size measurements are defined in Section 9.1.3).
- To correlate IAB2M positivity (SUV) and Gleason pattern (3, 4 and 5):
  - The Spearman-rank correlation coefficient will be used to evaluate the association between correlate SUV and the histopathologically defined Gleason pattern. The Wilcoxon rank-sum test will also be used to compare  $\text{SUV}_{\text{max}}$  measurements between lesions with low Gleason score (3+4 or lower) and high Gleason score (4+3 or higher).
- To correlate IAB2M positivity (SUV) and PSA:

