  - The Spearman-rank correlation coefficient will be used to evaluate the association between SUV and serum PSA levels obtained during screening.
- To determine the ability of *in vivo*  $^{89}\text{Zr}$ -df-IAB2M PET/CT to identify extra-prostatic extension:
  - The Wilcoxon rank-sum test will be used to compare  $\text{SUV}_{\text{max}}$  measurements of IAB2M-positive extra-prostatic sites between lesions with and without histopathologically confirmed extra-prostatic extension.
- To determine the ability of *in vivo*  $^{89}\text{Zr}$ -df-IAB2M PET/CT to identify occult lymph node involvement:

- The Wilcoxon rank-sum test will be used to compare  $SUV_{max}$  measurements of IAb2M-positive lymph nodes between patients with and without histopathologically confirmed lymph node involvement.
- To further evaluate the safety of  $^{89}Zr$ -DF-IAB2M PET/CT and  $^{68}Ga$ -PSMA-HBED-CC imaging.
  - See section on Risks

Additionally, we will assess whether there is improved sensitivity in detecting localized PCa by combining imaging results. This assessment will be done by estimating the PPV with different combinations of imaging modalities. The incremental effect of an additional imaging modality on PPV will be tested with the Wald test, as described by Turkbey B, et al.

All p-values will be two-sided with statistical significance evaluated at the 0.05 alpha level. All analyses will be performed in SAS Version 9.4 (SAS Institute, Inc., Cary, NC) and Stata Version 13.0 (StataCorp, College Station, TX).

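### Section 1.2 asks for the proportion of lesions positive on IAB2M by size, Gleason pattern and PSA, but section 12.1 analyses SUV intensity, and no planned analysis relates detection to PSA

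*Combined protocol and SAP*

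**What the plan says.** Section 1.2 of the combined protocol and SAP lists as a secondary objective: "Determine the proportion of IAB2M positivity (as measured by SUV) versus lesion size, Gleason pattern, and PSA levels". Correlation of PET findings with pathological features is already a separate objective, the first in that list.

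In section 12.1, under Secondary endpoints, the proportion objective becomes three correlation endpoints:

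- Size: "The Spearman-rank correlation coefficient will be used to evaluate the association between SUV and size of the lesion".
- Gleason: a Spearman coefficient between "SUV and the histopathologically defined Gleason pattern", plus a rank-sum test of SUVmax for lesions scored 3+4 or lower against 4+3 or higher.
- PSA: a Spearman coefficient for the "association between SUV and serum PSA levels obtained during screening".

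Detection as a yes/no outcome appears under the first secondary endpoint: "The Wilcoxon rank sum test will be used to compare lesions that were and were not identified on" PET. The features compared are lesion size, PSMA staining and Gleason score. PSA is not among them.

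Section 12.1 also plans sensitivity, specificity, PPV and NPV for lesions that are not clinically significant (below 0.5 cm³ with Gleason pattern below 4). Section 9.1.2.1 plans a lesion-by-lesion comparison with histology, primarily for tumors of at least 0.5 cm³ and secondarily for smaller ones. It defines a positive area visually, as uptake above adjacent or contralateral background, and records SUVmax and SUVmean for each such area. No SUV cut-off for positivity is given.

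**The concern.** A proportion positive and a correlation with SUV are different quantities. The first uses every histology-confirmed lesion as its denominator and asks how often PET finds it. The second asks whether uptake rises with size, grade or PSA. Either can be strong while the other is flat. If 12.1 is followed as written, a correlation coefficient would be reported against an objective that asks for a detection proportion.

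Section 12.2 says all estimates are preliminary data for future studies. Detection rate by size, grade and PSA is the kind of estimate a later study would take from this one, and a Spearman coefficient or a rank-sum p-value cannot be converted into it. The gap is widest for PSA, where the SUV correlation is the only planned analysis. That analysis pairs one PSA value per patient with SUV without saying which lesion's SUV is used.

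**Working it through.** **1. The plan's own figure.** Sections 12.1 and 12.2 state ±19.0 points for the primary proportion with n = 20 and 75% success. The half-width is 1.96 × √(0.75 × 0.25 / 20) = 0.190, so the figure reproduces. The documents give no figure for this secondary objective.

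**2. What each planned analysis delivers for it.**

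| Factor | SUV analysis | Detection analysis | Proportion positive by category |
|---|---|---|---|
| Size | Spearman | Rank-sum, identified v missed | Partial: sensitivity in the non-significant group; 0.5 cm³ split in 9.1.2.1 |
| Gleason | Spearman; rank-sum of SUVmax, two groups | Rank-sum, identified v missed | None by pattern 3, 4, 5 |
| PSA | Spearman | None | None |

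The non-significant group combines small size and low grade in one cell, so its sensitivity does not separate the two factors. The PPV and NPV analyses condition on the PET call and are not proportions of lesions detected.

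**3. Does intensity stand in for detection?** The documents do not give the number of lesions or any SUV distribution, so the following are assumptions.

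- Lesions: 20 to 60 in total, treated as independent.
- Detection: log-odds = 0.5 + slope × standardised log size, with slope 1.0 to 2.0.
- SUV in detected lesions: lognormal, median 5, log SD 0.5, unrelated to size.
- SUV in missed lesions: lognormal, median 2, log SD 0.3.
- 4,000 runs per setting, two-sided 0.05.

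| Lesions, slope | Detected above / below median size | Spearman, detected lesions only: mean (significant) | Spearman, all lesions: mean (significant) | Planned rank-sum of size, identified v missed: significant |
|---|---|---|---|---|
| 20, 1.0 | 76.3% / 44.5% | -0.01 (5%) | 0.29 (23%) | 41% |
| 40, 1.5 | 80.6% / 36.7% | 0.00 (5%) | 0.39 (73%) | 95% |
| 60, 2.0 | 84.1% / 31.1% | 0.00 (5%) | 0.46 (97%) | 100% |

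With the same detection pattern, the correlation is null or clear depending on whether missed lesions receive an SUV.

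The converse also holds. Suppose every lesion is positive, log SUV = 0.25 × log size + error with SD 0.4, and log size has SD 1 (assumed). The Pearson correlation is 0.25 / √(0.25² + 0.4²) = 0.25 / 0.472 = 0.53. Under normality the Spearman value is (6/π) × arcsin(0.53 / 2) = 0.51. Detection is 100% at every size, yet the coefficient is about 0.5.

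**4. Precision of the missing estimates.** At 75% positive, ignoring clustering:

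- 20 lesions: ±19 points, as in step 1.
- 10 lesions: 1.96 × √(0.1875 / 10) = 0.268, or ±27 points.
- Exact 95% intervals: 9/10 gives 55% to 100%; 18/20 gives 68% to 99%.
- PSA split at the median, one result per patient, 10 v 10: the half-width of the difference is 1.96 × √(2 × 0.1875 / 10) = 0.380, or ±38 points.

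**The case against.** The strongest reply is that much of this is wording. The objective itself qualifies positivity as measured by SUV, and 12.1 restates it as correlating positivity (SUV) with each factor. Detection versus size and Gleason score is tested by the identified-versus-missed comparison. A proportion is planned for the non-significant lesions, and 9.1.2.1 already splits lesions at 0.5 cm³. The study is exploratory with 20 patients, so finer proportions would be imprecise.

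Most of this is correct and limits the point. It does not remove it. The rank-sum comparison gives a p-value rather than a proportion with an interval, belongs to another objective and omits PSA. The risk-group subgroups in 12.1 do not fill the gap: the groups are not defined in the text, and they apply to predictive values.

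A reader might infer that the plan only correlates SUV and leaves the objective wholly unanswered. The rank-sum test and the non-significant-lesion analysis rule that out. A reader might also infer that a strong size effect on detection would be reported as no association. That requires SUV to be taken only in PET-positive areas. Section 9.1.2.1 can be read that way, but 12.1 compares SUVmax in tumor and non-tumor regions, which suggests otherwise. Even under the restrictive reading, the planned rank-sum test would usually show the effect, except with few lesions and a weaker slope (41% in the first row of the table).

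The objection about precision stands. It argues for descriptive reporting and against a model with size, pattern and PSA together, which 20 patients cannot support.

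**Conclusion.** The point holds in limited form. The objective in 1.2 is a proportion, and the analyses assigned to it in 12.1 measure uptake intensity. For size and Gleason score the gap is partial: detection is tested, but no proportion is planned by Gleason pattern, and the only proportion specified for small lesions is for the combined small, low-grade group. For PSA the gap is complete as far as detection goes.

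The missing rule on SUV in PET-negative lesions is a second, linked weakness. Under the stated assumptions it moves the mean size correlation from 0.00 to between 0.29 and 0.46. Those values depend on assumed lesion counts, detection slopes, SUV distributions and independent lesions; the direction does not depend on their exact size.

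The primary endpoint is unaffected. The change is worth making because the study would otherwise not produce an estimate that its own objective names.

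**What to change.** In section 12.1, for this objective:

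1. Report the proportion of histology-confirmed lesions called positive on the ⁸⁹Zr PET/CT read, with 95% intervals that allow for several lesions per patient, by size (below 0.5, at least 0.5 cm³), by highest Gleason pattern (3, 4, 5) and by PSA (below or above the cohort median). Name which of the two reads in 9.1.2.1 supplies the call.
2. If a model is wanted, use the logit GEE already named in 12.1 with one factor at a time, labelled descriptive.
3. State that SUV is measured in every histology-confirmed lesion, including PET-negative ones. Keep the Spearman coefficients as supporting results, and say which lesion's SUV is paired with PSA.

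The cost is a short edit to 12.1. The lesion list (9.1.4.1), the PET map (9.1.2.1) and screening PSA are already collected; the only added work is placing SUV regions on missed lesions. The downside is wide intervals, as in step 4 of the working, and wider still if results cluster within patients. If only uptake intensity is of interest, the alternative is to reword the objective in 1.2 to say so.

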## 2. BACKGROUND

### 2.1 Disease

Localized PCa is presently evaluated by serum prostate specific antigen (PSA) sampling and transrectal ultrasound (TRUS) and magnetic resonance (MR) imaging, both of the latter being anatomic approaches. As a secretory protein, PSA does not provide anatomic details nor does it distinguish between malignant or benign pathology. TRUS and MR imaging modalities are limited by their inability to identify and differentiate localized malignant tissue from common benign pathology, i.e., benign prostatic hyperplasia, inflammation, etc. Furthermore, the images created are poorly defined and subject to artifact. The present inability to clearly image and identify malignant tissue and to localize the site/s of disease leads to unnecessary biopsy of many patients [1,000,000 prostate biopsies per year in US] and an inability to direct the biopsy towards any suspicious site/s. As a direct result, the substantial majority of prostate biopsies are negative, suggesting that there was no need for the biopsy or that the biopsy failed to sample the lesion. Nevertheless, the biopsied patients are subject to potentially significant morbidity and even mortality.

An imaging modality that is able to selectively identify malignant prostatic tissue within the

gland, would allow for accurate, targeted biopsies of suspicious foci and would reduce unnecessary biopsies in patients with benign pathologies. The modality would also allow for improved clinical staging and risk stratification, improved monitoring of patients on active surveillance and improved targeting of focal therapy.

### Prostate Specific Membrane Antigen (PSMA)

PSMA is the single, most well-established, highly restricted prostate epithelial cell membrane antigen known. Although first thought to be entirely prostate-specific, subsequent studies demonstrated that PSMA is also expressed by some brain astrocytes and cells of the small intestine, proximal renal tubules and salivary glands. However, the level of expression in these non-prostate tissues is between a hundred-fold to a thousand-fold less than in prostate tissue and the site of PSMA expression in these normal cells (brush border/luminal location) are not readily accessible to circulating antibodies because of the blood: brain barrier or, in the case of the epithelial locations, due to intervening cell layers, basement membrane and epithelial tight junctions.

In contrast to other well-known prostate-restricted molecules such as PSA and prostatic acid phosphatase (PAP), which are secretory proteins, PSMA is a type II integral cell-surface membrane protein that is not secreted. Pathology studies indicate that PSMA is expressed by virtually all prostate cancers and PSMA expression increases progressively in higher grade cancers, metastatic disease, and hormone-refractory prostate cancer. These qualities make PSMA an ideal target for monoclonal antibody (mAb) imaging and/or therapy.

## 2.2 **Investigational Agent**

### Humanized J591 (huJ591)

The huJ591 mAb is a de-immunized monoclonal antibody directed at the extracellular domain of human PSMA. huJ591 was derived from murine J591 using Biovation's DeImmunization technology (Biovation, Aberdeen, Scotland, UK). In this technology, individual amino acids in predicted B and T cell epitopes were replaced with alternative amino acids such that the murine epitopes are no longer immunogenic to the human immune system. The modification results in a non-immunogenic antibody that may be administered to patients on multiple occasions and over long periods without inducing an immune response. huJ591 is produced from NS0 cells by Lonza (Lonza Biologics, Slough, UK).

The humanized version of J591 has provided promising results in imaging both localized PCa and metastatic disease. Initial phase I/II studies using huJ591 trace-labeled with Indium (In) and Lutitium (Lu) using a DOTA chelate showed that repetitive dosing was well tolerated without the development of a human anti-humanized antibody (HAHA) response. No dose limiting toxicity occurred at imaging doses of radionuclide conjugates and the maximum tolerated dose was not reached. Excellent tumor targeting could be detected at all dose levels of the mAb. No mAb targeting to sites other than those involved by PCa was observed although, as seen in other trials using radiometals, the liver is the primary site of

radiometal metabolism. Percent injected dose in the liver diminished with increasing dose of cold huJ591, and higher doses were associated with longer plasma clearance times.

[figure not shown]
### Humanized J591-Minibody (IAB2M)

IAB2M is an engineered antibody fragment (derived from huJ591) that targets the extracellular domain of the PSMA. The intact parental huJ591 antibody demonstrated sufficient tumor uptake to be useful as an imaging and therapy agent, however, the prolonged blood circulation time leads to increased background activity and radiation dose to normal organs thereby, somewhat limiting the imaging or therapeutic potential of these agents. Radiolabeled engineered antibody fragments have much faster clearance rates, providing improved tumor-to-blood ratios. However, fragments below 60 kDa are filtered through the glomerulus, leading to significant renal excretory activity, which is an unfavorable characteristic for a PCa imaging agent as the radioactivity within the bladder interferes with imaging of the adjacent prostate. To address these issues, IAB2M was engineered by fusing VH-linker-VL-CH3 gene segments, producing a single-chain protein that self-assembles into a small, stable, bivalent imaging agent with a molecular weight of approximately 80 kDa. The minibody format is half the size of complete, full-length antibodies, yet retains full bivalent binding to the target and is not excreted via the glomerulus.

Previous studies with a radiolabeled minibody demonstrates rapid biodistribution, efficient target penetration, and rapid blood/background clearance due to the smaller size, allowing high-contrast images to be obtained within hours after injection compared to the current delay of several days to a week when intact antibodies are used for imaging. The lack of CH2 domain in the minibody format removes antibody effector functions, removes FcRn-mediated prolongation of plasma half-life, and the risk of an immunologic response such as complement-dependent cytotoxicity is reduced to negligible. For functional imaging purposes, IAB2M is conjugated to desferrioxamine (Df) and radiometal labeled with Zr (T1/2 78.41 hours). The end product, Zr-df-IAB2M, is non-immunogenic, recognizes an extracellular target, is not excreted via the kidney, and exhibits rapid kinetics desirable for imaging.

### Engineering the IAB2M Minibody

The DNA sequences of the heavy and light chains for the humanized anti-PSMA antibody huJ591 were provided by [name] (Weill Cornell Medical College). ImaginAb, the creators and IND owners of IAB2M, re-humanized the DNA sequences using a later generation approach. The variable genes from the heavy and light chain DNA were separately amplified and joined together by overlap PCR to form a single-chain Fv (scFv) with an 18 amino acid linker. This scFv fragment was subsequently fused to the human IgG1 CH3 domain via the human IgG1 hinge sequence by overlap PCR to form the complete minibody (scFv-CH3 dimer) construct (see Figure 1).

**Figure 1.** The anti-PSMA minibody is a covalent bound dimer of two single-chains composed of a scFv fused to the human IgG1 hinge-CH3 region. The scFv is the huJ591 variable heavy chain (VH) and light chain (VL) connected by a linker. PSMA, the target antigen, is represented by the gray rectangles at the top.

A cGMP Master Cell Bank (MCB) was created from a stable cell pool at Catalent BioPharma (Middleton, WI). IAB2M was developed in their proprietary GPEX® technology, a high-titer retroviral vector that generated a stable CHO cell line. Full MCB testing has been completed, along with viral clearance. Subsequently a cGMP production run was initiated in the GMP suite from the MCB for the production of IAB2M. IAB2M was released by Catalent BioPharma against qualified release assays for conjugation. cGMP grade Df was obtained (Macrocylics, Dallas, TX). In the GMP suite at Isotherapeutics Group (Angleton, TX), Df-IAB2M was manufactured and sent out for final safety as well as release testing. In the GMP suite, vials of Df-IAB2M were filled and finished.

### Pre-clinical Studies: Functional Characterization of IAB2M

Full characterization of IAB2M was carried out, including a comparison with huJ591. IAB2M binding to PSMA has been confirmed by ELISA and flow cytometry in competition with huJ591. In vitro, *ex-vivo* and *in vivo* internalization assays demonstrate internalization that is comparable to huJ591 (unpublished data).

Serial PET/CT studies on mice with PSMA+ and PSMA- xenografts showed up to 13.25%ID/g uptake in PSMA+, as compared with nominal uptake in PSMA- xenografts. Background activity was observed in the liver (15-20%ID/g), as expected, since the primary route of clearance for minibodies and radiometals is hepatic. Small animal PET/CT studies comparing a labile (I-124) versus residualizing (radiometal/chelater) radiolabeling strategy indicates that as much as 75% of IAB2M is internalized over a 48-hour time period (unpublished data).

### Amendment v3 (01/27/17):

#### Ga-PSMA-HBED-CC (Ga-PSMA)

PSMA has recently been discovered as a promising target for radioisotope based approaches, both for PET imaging, for example, using Ga-labeled PSMA ligands. All of these trials report retrospective data on case reports/case series. No well-designed prospective clinical trial has been published/reported yet.

During the last two decades, many efforts have been undertaken to develop PSMA-ligands. One of these ligands, the small molecule Glu-NH-CO-NH-Lys-(Ahx)-[Ga(HBED-CC)], also known as PSMA-11®, PSMAHBED, Glu-CO-Lys(Ahx)-HBED-CC, DKFZ-PSMA-11, PSMA-HBED- CC, PSMA-HBED, PSMA or Prostamedix™, developed at the German Cancer Research Center Heidelberg (DKFZ), has become the most clinically used radiotracer. This compound shows a strong binding affinity to PSMA as well as a highly efficient internalization into PCa cells. PET/CT-imaging with Ga-PSMA-11 has demonstrated this novel method as an important imaging modality for diagnosing recurrent PCa. Perera et al., did systematic review of Ga-PET articles and Sixteen articles involving 1309 patients were analyzed. On per-patient analysis, the summary sensitivity and specificity were both 86%. On per lesion analysis, the summary sensitivity and specificity were 80% and 97%, respectively.

ABX Advanced Biochemical Compounds, Radeberg, Germany produces PSMA-HBED-CC for clinical use. Upon purchase and shipment to Weill Cornell Medicine, the peptide will be labeled with Ga with the final product being Ga-PSMA-HBED-CC. Radionuclide conjugation will be done at the Division of Nuclear Medicine, Department of Radiology, Weill Cornell Medicine.

The material produced are subjected to quality assurance testing as outlined in the Food and Drug Administration “Points to Consider”. All production data and supporting documents, together with the results of all quality assurance testing, have been provided to and reviewed by the Food and Drug Administration (Ga-PSMA-HBED-CC, IND# 124495).

